12.2 General statistical considerations

Statistical analysis and generation of tables, figures, and subject data listings will be performed using SAS[®] Version 9.1.3 or higher. All statistical tables and listings will use Courier New, font size 9.

All variables will be analyzed in an explorative manner using descriptive statistics only. Summary statistics will consist of frequency tables for categorical variables. For continuous variables, descriptive statistics (number of available observations, mean, and median, standard deviation, minimum and maximum) will be tabulated.

For analyses by visit, visit will be used as documented.

The Baseline value for all analyzed variables is the measured value at Visit 1 (V1) in Week 0.

12.3 Planned efficacy analyses

12.3.1 Analysis of the primary efficacy variable

A patient is defined to have reached clinical remission if they show a DAS28 of <2.6. The absolute and relative number of patients in remission will be presented. Additionally, the respective 95% confidence interval (CI), constructed from an approximation to the Normal distribution, will be determined for the remission rate.

Evaluation will be done for subgroups defined by the following variables:

• Response at Visit 2 or Visit 3 (after approximately 6 and/or 12 weeks) defined by reduction in DAS28 by ≥1.2

Confidential Page 35 of 89

- Presence of relevant auto-antibodies at Baseline (cut-off depends on test used, eg, immunoglobulin M-RF enzyme-linked immunosorbent assay: ≥0.110 optimetric density; Latextest: >20IU)
- Presence of anticytoplasmatic antibodies (aCCP antibodies or anti-mutated citrullinated vimentin [MCV]); threshold for aCCP positive patient at Baseline >50Units; threshold for anti-MCV positive patient at Baseline >50Units/mL
- Pretreatments with other anti-TNF agents
- Pretreatments with other biologics
- Duration of RA disease (<2 years vs. ≥2 years)

The remission rates between subgroups and their associated 95% CIs will be compared numerically only.

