5.1.2 Number of planned patients and sites

Physicians treating RA patients with biologics will be invited to participate in this PASS. Appropriate selection of the study sites will ensure collection of data representative for the general RA population.

The study will be conducted at approximately 160 sites in Germany. A total of 1068 patients are planned to be enrolled in this study, after the treating physician has made the decision to treat the patient with CZP.

Confidential Page 17 of 89

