9.11 C-Reactive Protein and Erythrocyte Sedimentation Rate

C-reactive protein levels or ESR rate will be analyzed by a local laboratory. The preferred assessment is CRP; alternatively ESR can also be obtained, as long as the assessment is consistent throughout the course of the study.

Confidential

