12.7 Determination of sample size

As no information on the expected remission rate for a 2-year study under real life conditions are available, an overall remission rate of 50%, which is the worst case for sample size calculation, was used for determination of sample size. Assuming this remission rate, a total of 1068 patients is sufficient to estimate with 95% confidence the overall remission rate with a precision of $\pm 3.0\%$. Furthermore, subgroups of about 500 patients are sufficient to estimate the remission rate for each subgroup (as defined in Section 12.3.1) separately with an adequate precision ($\pm 4.5\%$).

In case the overall remission rate is much lower or higher (15% / 85%) a total of 1068 patients is sufficient to estimate with 95% confidence the overall remission rate with a precision of $\pm 2.1\%$.

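### The ±3.0% and ±2.1% precision in Protocol 12.7, and on its natural reading the primary 95% CI in 12.3.1, treat patients recruited through about 160 sites as independent; any positive within-site correlation makes that precision too favourable

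*Protocol*

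**What the plan says.** The primary variable is remission, DAS28 below 2.6, at Visit 9 (Protocol 4.1.1). Section 12.3.1 reports the number and proportion in remission and adds that "the respective 95% confidence interval (CI), constructed from an approximation to the Normal distribution, will be determined for the remission rate". The same intervals are given for subgroups, which are compared by eye only. The section names no variance estimator and does not mention site.

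Section 12.7 plans on "an overall remission rate of 50%, which is the worst case for sample size calculation" and states that "a total of 1068 patients is sufficient to estimate with 95% confidence the overall remission rate with a precision of" ±3.0%. It gives ±2.1% for a rate of 15% or 85%, and ±4.5% for subgroups of about 500. It mentions no site effect, ICC or design effect.

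On recruitment, section 5.1.2 says: "The study will be conducted at approximately 160 sites in Germany". It also says: "A total of 1068 patients are planned to be enrolled in this study". The same section expects the choice of sites to make the data speak for RA patients in general.

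**The concern.** Patients are reached through invited physicians, and several determinants of the outcome act at physician or site level:

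- The treating physician evaluates efficacy (5.1.1).
- The acute-phase component of DAS28 is measured locally: "C-reactive protein levels or ESR rate will be analyzed by a local laboratory" (9.11). Either CRP or ESR may be used.
- CZP treatment and concomitant medication are left to the physician (5.1, 7.7.1).
- Assessments are recorded only where they belong to local routine (5.2, footnote a).

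Positive correlation of remission within site is therefore plausible. The result is meant to apply beyond the participating sites, so between-site variation belongs in its variance. A simple binomial variance has no such component. Changing the form of the interval, for example to Wilson or exact on the pooled count, would not add one.

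The remission rate and its interval are the whole primary result, and precision is the only basis given for the sample size.

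**Working it through.** **Inputs from the protocol.** N = 1068 and about 160 sites (5.1.2); rates of 50% and 15%/85%, 95% confidence, ±3.0% and ±2.1% (12.7). Mean site size m = 1068/160 = 6.675.

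**Assumed inputs.** ICC from 0.01 to 0.10, and the coefficient of variation (CV) of site size. The protocol gives neither. All 1068 patients are taken as analysed unless stated.

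**Step 1: reproduce the plan's figures under independence.**

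- n = 1.96² × 0.25 / 0.03² = 1067.07, rounded up to 1068.
- Half-width at 50%: 1.96 × √(0.25/1068) = ±3.00%.
- Half-width at 15% or 85%: 1.96 × √(0.1275/1068) = ±2.14%, stated as ±2.1%.
- Subgroup of 500 at 50%: 1.96 × √(0.25/500) = ±4.38%, inside the stated ±4.5%.

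The overall figures match with a design effect of exactly 1.

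**Step 2: allow for sites.**

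- DEFF = 1 + ((1 + CV²) × m − 1) × ICC
- True half-width = 1.96 × √(p(1−p) × DEFF/1068)
- Coverage of the unadjusted interval = 2Φ(1.96/√DEFF) − 1

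Example with equal sites and ICC 0.05: DEFF = 1 + 5.675 × 0.05 = 1.284; half-width = 3.00% × √1.284 = 3.40%; coverage = 2Φ(1.96/1.133) − 1 = 91.6%.

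| ICC (assumed) | Site-size CV (assumed) | DEFF | Half-width at 50% | Coverage of unadjusted CI |
|---|---|---|---|---|
| 0 | any | 1.00 | ±3.00% | 95.0% |
| 0.01 | 0 | 1.06 | ±3.08% | 94.3% |
| 0.02 | 0 | 1.11 | ±3.16% | 93.7% |
| 0.05 | 0 | 1.28 | ±3.40% | 91.6% |
| 0.10 | 0 | 1.57 | ±3.75% | 88.3% |
| 0.01 | 0.8 | 1.10 | ±3.14% | 93.8% |
| 0.05 | 0.65 | 1.42 | ±3.6% | 90% |
| 0.05 | 0.9 | 1.55 | ±3.7% | 88% |
| 0.10 | 0.8 | 2.00 | ±4.24% | 83.5% |

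At a 15% or 85% rate and ICC 0.05, the half-width is 2.14% × √1.284 = ±2.4% with equal sites and 2.14% × √1.554 = ±2.7% at CV 0.9.

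**Step 3: check by simulation.** With 160 sites of 6 or 7 patients, beta-binomial site rates, a 50% rate and 40,000 runs, the unadjusted interval covered 94.6% at ICC near 0, 94.0% at 0.01, 93.1% at 0.02, 91.0% at 0.05 and 87.6% at 0.10. This agrees with the formula to within about one percentage point.

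**Step 4: subgroups.** For 500 patients spread evenly over 160 sites, m = 3.125. At ICC 0.05, DEFF = 1 + 2.125 × 0.05 = 1.106 and the half-width is ±4.6%, against ±4.38% under independence. The effect is smaller because fewer patients share a site.

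**Step 5: what a clustered interval does.** In a separate simulation (160 sites, 6000 runs per scenario, 50% rate, ICC 0.05), an interval with site as the cluster covered 94.8–95.1% for site-size CVs from 0 to 0.91, with mean half-widths of 3.42% to 3.74%. At ICC 0 its half-width was 3.01–3.02%, against 3.00% unadjusted.

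**The case against.** **12.3.1 fixes only a Normal approximation.** A site-robust standard error with a Normal critical value would satisfy that wording, and section 12 leaves further detail to the SAP, which is not at hand. This stands. A reader might infer that the protocol prescribes a defective interval. It does not say so; independence is demonstrated for 12.7 and is only the natural reading of 12.3.1. If a clustered variance is intended, 12.7 quotes the wrong precision for it.

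**The loss depends on an ICC that the documents do not give.** This also stands. A reader might infer that the interval is certainly too narrow, or that coverage falls by five points. At ICC 0.01 the effect is immaterial. A five-point loss at ICC 0.05 needs a site-size CV of about 0.64 as well; with equal sites the loss is about 3.4 points. What remains is conditional, but its direction is the same for every positive ICC.

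**Fewer than 1068 may be analysed.** The Full Analysis Set (12.1) requires a DAS28 of at least 2.6 and a valid post-Baseline value, and assessments depend on routine practice. Fewer patients per site lower the design effect. If half contributed (an assumption), m would be about 3.3, DEFF at ICC 0.05 with equal sites about 1.12, and coverage about 93.6%. This reduces the clustering loss but does not rescue ±3.0%, because a smaller N widens the interval for its own reason.

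**A 50% rate is the worst case, so there is slack.** At ICC 0.05 with equal sites, the half-width stays within ±3.0% for rates below about 26% or above about 74%. That is true, but 12.7 states its precision at 50% and at 15%/85%, and each figure is affected.

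**Sites are selected, not randomly sampled.** The inference target is then partly a choice. But 5.1.2 aims the result at RA patients in general, which favours counting between-site variation.

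**Conclusion.** The point holds in conditional form. The ±3.0% and ±2.1% in 12.7 assume independent patients, with no allowance for about 160 sites, and 12.3.1 read naturally does the same. If remission is positively correlated within site, the stated precision is too favourable and an unadjusted interval covers less than 95%.

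The loss is negligible at ICC 0.01 and becomes material from about 0.05, or with very unequal site sizes. These sizes rest on assumed ICC and site-size variation and on all 1068 being analysed.

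A reader might also infer that the study is too small or that its conclusions would be wrong. Neither follows. Section 12.2 makes all analyses descriptive, with no test or success threshold, so the consequence is overstated precision, not a false decision.

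**What to change.** - **12.3.1:** keep the pooled remission rate as the estimate. Compute its 95% CI, and the subgroup CIs, with a variance that takes site as the cluster and t on (sites − 1) degrees of freedom. A Taylor-linearised or sandwich variance would do, for example SAS PROC SURVEYFREQ with site as CLUSTER. No ICC has to be assumed for this.
- **12.7:** state that ±3.0% and ±2.1% assume independent patients. Add the clustered range with its assumed ICC and site-size variation: for example, at ICC 0.05 and site-size CV from 0 to 0.9, about ±3.4% to ±3.7% at a 50% rate and ±2.4% to ±2.7% at 15%/85%.

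The cost is a short change of wording and one change of procedure, using the site identifier already in the data. The downside is a somewhat wider reported interval and a less favourable stated precision. No extra patients or data are needed.

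### Section 12.3.1 fixes a Normal-approximation 95% CI that is adequate at the planned sizes but under-covers, or gives impossible limits, if a subgroup turns out small; naming the Wilson interval costs almost nothing.

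*Protocol*

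**What the plan says.** Protocol section 12.3.1 reports the number and percentage of patients in remission, with a two-sided 95% interval "constructed from an approximation to the Normal distribution". It then states: "Evaluation will be done for subgroups defined by the following variables". Six variables follow: early DAS28 response, auto-antibodies, anticytoplasmatic antibodies, earlier anti-TNF treatment, earlier treatment with other biologics, and disease duration. On reading the subgroups it says: "The remission rates between subgroups and their associated 95% CIs will be compared numerically only". It names no separate interval method for subgroups and sets no minimum subgroup size.

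Section 12.7 bases the sample size on "an overall remission rate of 50%, which is the worst case for sample size calculation", and also gives the precision at overall rates of 15% and 85%. For subgroups it says that "subgroups of about 500 patients are sufficient to estimate the remission rate for each subgroup", with a stated precision of ±4.5%. Section 12.2 makes every analysis exploratory and descriptive.

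**The concern.** The interval method is a stated choice, not something left open. The simplest Normal-approximation interval (Wald) is known to cover too little when the group is small and the rate is near 0 or 1.

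Subgroup sizes here are whatever the six splits yield. Two levels of about 500 need a nearly even split (1068 / 2 = 534), and nothing in the protocol makes all six splits even. No test is planned, so the interval is the only stated measure of uncertainty when subgroup rates are set side by side. If it is too narrow, a small subgroup looks more precise than it is. A negative limit or a zero-width interval would also be an avoidable blemish in a results table.

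**Working it through.** **Inputs from the protocol.** Two-sided 95% level and Normal approximation (12.3.1); N = 1068, subgroups of about 500, rates of 15%, 50% and 85% (12.7). The protocol does not name the formula. Wald is assumed because it reproduces the figures in 12.7.

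**1. The protocol's own figures.** The half-width is 1.96·√[p(1−p)/n].
- N for ±3.0% at p = 50%: 1.96² × 0.25 / 0.03² = 1067.07, rounded up to 1068. Reproduced.
- p = 15% or 85%, n = 1068: ±2.14% (stated ±2.1%). Reproduced.
- p = 50%, n = 500: ±4.38% (stated ±4.5%, which needs only 475). Consistent.

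**2. Coverage at the stated inputs.** Exact coverage is the sum of the binomial probabilities of all counts x whose interval contains the true p. For Wald, over p from 15% to 85%:

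| n | Minimum | Mean |
|---|---|---|
| 1068 | 94.5% | 95.0% |
| 500 | 94.2% | 94.9% |
| 200 | 93.3% | 94.7% |

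At n = 500 and a rate of 15% or more, the chance of a limit outside 0-100% or of zero width is below 0.0001.

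**3. Coverage in small subgroups.** The sizes of 100 or fewer and the rates below 15% are assumptions. For scale, a subgroup holding 5-10% of 1068 patients would have 53 to 107. For true rates of 10% to 20%:

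| n | Wald mean | Wald minimum | Wilson mean |
|---|---|---|---|
| 100 | 93.7% | 91.1% | 95.1% |
| 50 | 92.2% | 87.9% | 95.2% |
| 30 | 89.9% | 80.9% | 95.4% |

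Single points vary, because binomial coverage jumps with n and p. At n = 50, Wald covers 87.9% at p = 10% but 94.1% at p = 15%. At n = 100 and p = 5% it covers 87.8%, against 96.6% for Wilson.

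**4. Impossible or zero-width intervals.** The Wald lower limit is negative when x/n < 1.96·√[x(n−x)/n³], that is, when 0 < x < 3.84·n/(n+3.84). At n = 20, 30, 50, 100 and 500 this means 1, 2 or 3 remitters. With none, or all, in remission the width is zero.
- 3 of 50: 6.0% ± 1.96·√(0.06 × 0.94 / 50) = 6.0% ± 6.6%, so −0.6% to 12.6%. Wilson gives 2.1% to 16.2%.
- 0 of 20: Wald gives 0% to 0%. The Wilson upper limit is 3.84 / (20 + 3.84) = 16.1%.
- Chance of a negative lower limit: 61% at n = 30 and p = 10%; 31% at n = 30 and p = 15%; 25% at n = 50 and p = 10%.

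**5. Effect of changing method at the planned sizes.** The Wilson half-width at p = 50% is 2.99% at n = 1068 (Wald 3.00%) and 4.37% at n = 500 (Wald 4.38%).

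**The case against.** The strongest defence is that the protocol expects subgroups of about 500, where the interval works. Groups of 20, 30 or 50 and rates of 10% appear nowhere in it. The 15% and 85% in 12.7 are overall rates used to show precision at 1068, not predictions for small groups. Even at n = 30 and a true rate of 15%, Wald coverage is 94.2%, and the chance of no remitters is only 0.85³⁰ = 0.8%. All of this stands, and it is why the point is conditional. It does not remove the point: 12.7 says that about 500 is sufficient for a given precision, which neither sets nor guarantees a size.

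Second, a Normal approximation need not mean Wald. The Wilson interval also derives from one and would arguably fit the wording, and section 12 leaves detail to the SAP. This stands too, and makes the change a clarification as much as a correction.

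Third, the comparison is descriptive, no decision depends on it, and counts are shown, so a reader would see 0 of 20 beside a zero-width interval. That limits the harm. Nor is Wilson better at every point: at n = 200 and p = 15% it covers 94.1%, against 94.5% for Wald. Its advantage is in average coverage and in avoiding impossible limits.

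A reader might infer that the planned subgroup intervals cover well below 95% as they stand, or that the primary estimate is unreliable. The documents support neither: both would need sizes or rates outside those stated.

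**Conclusion.** The point holds as a minor, conditional improvement. At the stated sizes and rates the interval is sound (coverage at least 94.2%), and the overall remission rate and sample size are unaffected. If a subgroup turns out small (roughly 100 or fewer with a rate near 10-15% or below, or 50 or fewer), mean coverage over rates of 10-20% falls short of 95% by about 1 point at n = 100, 3 points at n = 50 and 5 points at n = 30. With 0 to 3 remitters the limits can be negative or the width zero.

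This rests on three assumptions: that the Wald form is meant, that the subgroups inherit it, and that at least one of the six splits is very uneven. The protocol gives no prevalence by which to judge the last.

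**What to change.** In section 12.3.1, replace the reference to a Normal approximation with the Wilson score 95% confidence interval, for the overall remission rate and for every subgroup rate. A Clopper-Pearson interval would also remove negative limits and zero widths.

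The cost is one line of wording and one software option. Section 12.7 can stay as it is, since 1068 patients still give a half-width of 2.99% at a 50% rate. Some small-subgroup intervals will become slightly wider or shift.

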5.2 Schedule of study assessments

The schedule of study assessments by visit are presented below.

Assessments ^a	Treatment period ^b							Safety Follow -Up		
Visit	V1	V2	V3	V4	V5	V6	V7	V8	V9	V10
Week	0	6	12	24	36	52	64	76	104	116
Written Data Consent ^c	X	X								
Demographics / Medical History	X									
Presence of Rheumatoid Factor	X									
Presence of anti-cyclic citrullinated peptide antibodies	X									
RA history	X									
Concomitant Medication	X	X	X	X	X	X	X	X	X	X
Adverse Events		X	X	X	X	X	X	X	X	X
Drug administration	X	X	X	X	X	X	X	X	X	
Joint scores (TJC, SJC) (28 joint count)	X	X	X	X	X	X	X	X	X	
Acute phase reactant (CRP or ESR)	X	X	X	X	X	X	X	X	X	
Morning stiffness	X	X	X	X	X	X	X	X	X	
Patient's Global Assessment of Disease Activity (VAS)	X	X	X	X	X	X	X	X	X	
Physician's Global Assessment of Disease Activity (VAS)	X	X	X	X	X	X	X	X	X	

Confidential Page 18 of 89

Assessments ^a	Treatment period ^b							Safety Follow -Up		
Visit	V1	V2	V3	V4	V5	V6	V7	V8	V9	V10
Week	0	6	12	24	36	52	64	76	104	116
Arthritis pain VAS	X	X	X	X	X	X	X	X	X	
Fatigue Assessment Scale	X	X	X	X	X	X	X	X	X	
HAQ-DI	X	X	X	X	X	X	X	X	X	
EQ-5D	X	X	X	X	X	X	X	X	X	
Sick leave	X	X	X	X	X	X	X	X	X	
Employment status and employability due to RA	X	X	X	X	X	X	X	X	X	
Information on subsequent RA treatment										X

CRP=c-reactive protein; EQ-5D=Euro Quality of Life – 5Dimensions; ESR= erythrocyte sedimentation rate; HAQ-DI; Health Assessment Questionnaire-Disability Index; RA=rheumatoid arthritis; SJC=swollen joint count; TCJ=tender joint count; V=Visit; VAS=Visual Analogue Scale

Confidential Page 19 of 89

^a Only if assessed as per current clinical practice. Since this is a noninterventional study, no additional diagnostic or monitoring procedure will be applied.

b Visits are recommended to be quarterly.

Written data consent will be obtained before any data are collected on study-specific forms. Written data consent may be obtained after the start of CZP treatment if the patient met all inclusion and exclusion criteria at the start of CZP treatment. For these patients, written data consent must be obtained at the start of Visit 2 and prior to conducting any clinical assessment at this visit.

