9.15 Presence of Rheumatoid Factor or Anti-cyclic Citrullinated Peptide Antibodies

The results of any previously recorded rheumatoid factors (RF) or anti-cyclic citrullinated peptide (aCCP) antibodies values are to be collected.

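### Section 12.3.1 fixes one positivity limit each for aCCP and anti-MCV without naming an assay, although the aCCP values are routine results already on file, so antibody subgroups may be misclassified

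*Protocol*

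**What the plan says.** Protocol Section 12.3.1 lists six variables by which the primary remission rate will be broken down. Two of them are antibody status, in adjacent bullets.

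- The first makes the limit a matter of the assay: "Presence of relevant auto-antibodies at Baseline (cut-off depends on test used, eg, immunoglobulin M-RF enzyme-linked immunosorbent assay". It gives two numerical examples on different scales: an optical density of at least 0.110 for the ELISA, and more than 20 IU for a latex test.
- The second gives fixed limits and names no assay: "threshold for aCCP positive patient at Baseline >50Units" and "threshold for anti-MCV positive patient at Baseline >50Units/mL".

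On where the values come from, Section 9.15 says: "The results of any previously recorded rheumatoid factors (RF) or anti-cyclic citrullinated peptide (aCCP) antibodies values are to be collected". Footnote a to the schedule in Section 5.2 adds that "no additional diagnostic or monitoring procedure will be applied". On the number of sites, Section 5.1.2 says: "The study will be conducted at approximately 160 sites in Germany". The schedule and the Visit 1 list in Section 8.1 describe the items as the presence of the antibodies. Section 12.2 defines Baseline generally: "The Baseline value for all analyzed variables is the measured value at Visit 1 (V1) in Week 0".

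**The concern.** A limit of 50 has meaning only for the assay and unit scale on which it was set. The protocol accepts this for the first antibody group and leaves it out for the second, yet both rest on whatever each site already has on file. No central assay, kit, conversion rule or laboratory limit appears anywhere in the protocol.

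If a laboratory's limit is below 50, a patient it reports as positive with a value between that limit and 50 is counted as negative. If the limit is above 50, the reverse happens. If a site holds only a positive or negative result, which is how the schedule words the item, the numerical rule cannot be applied at all.

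At stake is a planned breakdown of the primary variable. The subgroups are to be compared only by looking at the rates and their confidence intervals, so the displayed rates are the whole result. Bias from misclassification does not shrink with sample size, and the intervals do not show it.

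**Working it through.** **1. The plan's own figures.** Section 12.7 uses a normal-approximation interval for one proportion, n = z² × p(1 − p) / d².

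- With z = 1.96, p = 0.50 and d = 0.03, n = 1067.07, rounded up to 1068 as stated.
- For a subgroup of 500 at 50%, the half-width is 1.96 × √(0.25/500) = 4.38 points, against the stated 4.5.

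Neither figure depends on the antibody limit. They serve only as a yardstick.

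**2. Whether the aCCP values share one assay.** Section 9.15 takes earlier results as they stand, Section 5.2 rules out added testing, and about 160 sites contribute. Only CRP and ESR are expressly described as local laboratory results (Section 9.11). That aCCP comes from each site's own laboratory is therefore an inference, but these sections leave little alternative. The general Baseline rule in Section 12.2 does not change this, because no new antibody test is foreseen at Visit 1. For anti-MCV the support is weaker: Section 9.15 does not mention it, although the ban on added testing covers it.

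**3. What misclassification would do.** No error rate can be taken from the documents, so every input here is an assumption:

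- q = share of patients truly positive by their own laboratory's limit
- m = share of those counted as negative under the >50 rule
- f = share of true negatives counted as positive
- D = true difference in remission rate between the two groups, set to 10 points
- error unrelated to remission within each true group

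The displayed difference is D × (PPV + NPV − 1), where

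- PPV = q(1 − m) / [q(1 − m) + (1 − q)f]
- NPV = (1 − q)(1 − f) / [(1 − q)(1 − f) + qm]

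With f = 0 this reduces to D × (1 − q) / [(1 − q) + qm]. The remission rates enter only through D, so 55% against 45% gives the same result as 20% against 30%.

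Displayed difference in points, D = 10, f = 0:

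| q | m = 0 | m = 0.05 | m = 0.10 | m = 0.20 | m = 0.30 |
|---|---|---|---|---|---|
| 0.50 | 10.0 | 9.5 | 9.1 | 8.3 | 7.7 |
| 0.65 | 10.0 | 9.2 | 8.4 | 7.3 | 6.4 |
| 0.80 | 10.0 | 8.3 | 7.1 | 5.6 | 4.5 |

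Worked cell: q = 0.65, m = 0.10 gives 10 × 0.35 / (0.35 + 0.065) = 8.4.

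Error in the other direction only (m = 0, f = 0.05) gives 10 × q / [q + (1 − q) × 0.05] = 9.5, 9.7 and 9.9 points for q = 0.50, 0.65 and 0.80. Both errors together (m = 0.10, f = 0.05) give 8.5, 8.1 and 6.9 points. If every laboratory's limit equals the protocol's, m = f = 0 and nothing changes.

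**The case against.** The strongest case on the other side has four parts.

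- **The bullets do not literally contradict each other.** They cover different analytes, and the two rheumatoid factor examples sit on different scales, so they need different numbers in any case. A uniform limit across sites may be deliberate. This stands as far as it goes, but the protocol names neither an assay nor a reason, and nothing in it ensures that the recorded values share a scale.
- **Harm is not shown.** A reader might infer that patients are certain to be misclassified, or that the negative subgroup in particular will be contaminated. The documents do not support either. They give no laboratory or manufacturer limit, so both occurrence and direction are unknown. This stands in full.
- **The consequence is small.** A reader might infer that the study could fail to detect a difference. No test is planned: Section 12.2 makes all analyses descriptive. One subgroup variable of six is affected. In the table the negative-group rate moves by 10 minus the displayed difference, which in most cells is inside the 4.5 points that Section 12.7 calls adequate. At q = 0.80 and m = 0.30 it is 5.5 points. The limited consequence stands.
- **The SAP may deal with assays.** Section 12 defers detail to the SAP, which is not at hand. It may add handling of assays and units, but the limits themselves are fixed in the protocol.

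Laboratory calls are not neutral either, since they bring between-laboratory differences into the subgroup definition. Nor does Section 12.3.1 already use such calls for rheumatoid factor: it gives test-specific numbers as examples.

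**Conclusion.** The point holds as a risk built into a stated classification rule. Section 12.3.1 makes the limit test-dependent for one antibody group and fixes it at >50 for aCCP and anti-MCV with no assay named, while the aCCP values are routine results of unspecified origin. Where a laboratory's limit differs from 50, status may be wrong in either direction. The remission rates by antibody status would then usually be drawn towards each other. That direction assumes error unrelated to remission within each true group; if patients with values near the limit respond differently, it need not hold.

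The size is unknown. The range from 10 down to 4.5 points is illustration on assumed inputs, and it includes no effect. The overall remission rate, its interval and the sample size of 1068 are untouched. The case is firmer for aCCP than for anti-MCV, whose source the protocol does not describe. This calls for a correction of wording and data capture, not a change of design.

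**What to change.** In Section 12.3.1, make the aCCP and anti-MCV limits depend on the test, as for the other auto-antibodies. Classify each patient by the reporting laboratory's positive or negative call, or by its upper reference limit for the assay used. Record that call or limit next to the value, with assay and unit where available. Keep >50 only as a sensitivity display, or as a fallback when no call or limit is on file, and report how many patients were classified each way.

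The cost is a few sentences in an amendment or the SAP and, where not already captured, a field filled from existing laboratory reports. Since the schedule words the item as presence of the antibodies, some sites may already record the call. The drawbacks are that the call or limit may be missing for some older results, and that laboratory calls carry some between-laboratory variation.
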